Appendix 1. Symptoms and Adverse Events Following Non-invasive Auricular Vagus Nerve Stimulation

Participant ID: _____

Date: ______

		Severity	,		Persistence	Relatedness	
Symptom/Adverse Event	Tick on	e box per sy Mild	vmptom Moderate	Severe	Tick if symptom persisted after stimulation ceased (please detail duration of symptoms)	Tick if you believe that symptom is related to stimulation	Additional Comments
Redness/erythema							
Pain							
Irritation							
Ulcer							
Itching							
Dizziness							
Headache							
Fatigue							
Increased tinnitus							
Nausea							
Other events (please describe)							

22 November 23, Version 2

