The effect of non-invasive auricular vagus nerve stimulation paired with rehabilitation on gait and balance impairments in chronic stroke: A randomised controlled feasibility trial.

Primary investigator: [name] **Primary Supervisor:** [name] **Co-Supervisors:** [name], and [name]. [name], [name]

Innovation, Implementation and Clinical Translation (IIMPACT) in Health, Allied Health and Human Performance, University of South Australia

Background

Stroke is a leading cause of disability in Australia, costing the economy \$6.2 billion of direct cost and \$26 billion of indirect cost from lost wellbeing and mortality in 2020 [1]. Recovery from stroke mainly occurs in the subacute stage, driven by a period of enhanced neuroplasticity [2]. However, a large proportion of stroke survivors endure long-term impairments including limb weakness, impaired mobility and balance [1]. Hence, there is an imminent need for novel treatments to enhance stroke recovery. Recently, promising studies have demonstrated that pairing invasive vagus nerve stimulation (iVNS) with rehabilitation can enhance motor function post-stroke. For example, a multicentred, triple-blind, randomized controlled trial that included 106 stroke survivors with upper limb weakness has shown that iVNS paired with repetitive task training (for 6 weeks, 3 x 1 hour weekly) led to greater upper limb recovery compared to sham treatment [3]. Interestingly, the improvement in the active group was two to three times higher than the sham group, and more importantly, this effect was preserved for 90 days after treatment. Following this study, iVNS received approval from the Food and Drug Administration (FDA) as adjuvant therapy for chronic stroke rehabilitation [4]. However, iVNS is costly and requires a surgical procedure, limiting accessibility and imposing potential safety risks including symptomatic bradycardia, localised infection, and transient vocal cord palsy [3, 5, 6].

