Transauricular vagus nerves stimulation (taVNS) has been used successfully as a non-invasive, and potentially, safer alternative to iVNS as an adjuvant therapy for drug-resistant epilepsy and major depression [7, 8]. Recently, taVNS paired with rehabilitation was found to be a feasible and safe approach to improve upper-limb weakness in subacute [9] and chronic [6, 10] stroke. The first-in-human pilot study investigating taVNS to enhance upper-limb recovery in 14 adults with chronic stroke was conducted in 2017, showing that taVNS paired with robot-assisted rehabilitation was safe and feasible with effects in favour of the active compared to the sham group [6]. Similar results were observed in subacute stage of ischaemic stroke where taVNS paired with conventional rehabilitation improved upper-limb weakness in 21 people who received 30 minutes of taVNS followed by 30 minutes of conventional therapy for 15 consecutive days [9]. More importantly, the effect of taVNS was preserved 10 weeks from the end of the intervention. Although these early taVNS studies in stroke shared some key limitations, including small sample size, the use of different stimulation parameters, and different sham protocols, their promising results, along with the good quality evidence for iVNS in stroke recovery, warrants further exploration of taVNS role in enhancing stroke recovery.

Altered gait and balance dysfunction are two common stroke-related deficits. Gait dysfunction occurs in more than 80% of people with stroke [11]. This leads to difficulty with mobility and performing activities of daily living [12]. Impaired balance is also common after stroke with 70% of people reporting a fall within 1 year of their stroke [11]. The positive effect of taVNS on upper-limb motor function, likely driven by enhanced neuroplasticity [13, 14], suggests that pairing taVNS with other therapies might prove beneficial. However, the effect of taVNS combined with gait/balance training to enhance recovery of the lower limb has not been studied. This research aims to assess the feasibility, safety, and preliminary efficacy of taVNS

paired with rehabilitation for enhancing gait and balance impairments in people with chronic stroke (> 6 months).

Method:

Aim: The primary aim is to assess the feasibility and safety of taVNS to enhance gait and balance impairments in people with chronic stroke. The secondary aim is to gain preliminary data about the efficacy of taVNS in this population.

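### The weekly adverse event form has no prompt for falls, so falls outside sessions of a gait and balance trial rely on a free-text row

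*Protocol*

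**What the plan says.** The Aim paragraph states: "The primary aim is to assess the feasibility and safety of taVNS to enhance gait and balance impairments in people with chronic stroke". Under Outcome Measures, the safety item names a purpose-built questionnaire, completed at the end of each week, and asks participants to tell the treating physiotherapist at once about any adverse event during a session. It says the form was developed from the team's scoping review and guided by a systematic review of taVNS safety.

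The form is headed "Appendix 1. Symptoms and Adverse Events Following Non-invasive Auricular Vagus Nerve Stimulation". Its ten named rows are redness/erythema, pain, irritation, ulcer, itching, dizziness, headache, fatigue, increased tinnitus and nausea. The last row is "Other events (please describe)". Besides severity, there is one column for whether the symptom outlasted the stimulation and one for whether the participant believes the stimulation caused it.

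On falls, the Background says: "Impaired balance is also common after stroke with 70% of people reporting a fall within 1 year of their stroke". Entry requires a gait and/or balance impairment, and participants may need an aid or assistance to walk 10 metres. Rehabilitation is 15 one-hour sessions over 6 weeks.

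The last row of Table 1 turns adverse events into a progression criterion: Proceed if fewer than 20% of participants have a moderate to severe event. It does not restrict these to events related to stimulation.

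**The concern.** The intervention under test is stimulation combined with gait and balance training, but the form is built around stimulation alone. Falls are a readily foreseeable harm in this population doing this training, and they have no row. Someone who trips at home and then meets a form about symptoms following ear stimulation has little reason to write the fall in. No other instrument in the protocol makes up for this: the efficacy outcomes include no count of falls, and the interview guide does not ask about them.

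At stake are the completeness of the descriptive safety summary, which answers half of the primary aim, and the count behind the Table 1 adverse event row. If falls go unrecorded, the trial cannot tell the designers of a larger study how often they happened or in which arm.

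**Working it through.** The protocol states no figure for adverse event capture or expected falls, so there is nothing to reproduce. The check compares the reporting routes and then gives an illustrative size.

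**Routes by which an event can reach the safety data**

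| Event | Named row on weekly form | Immediate report to physiotherapist | Open row |
|---|---|---|---|
| Listed symptom (e.g. dizziness) | yes | yes, if in session | not needed |
| Fall during a session | no | yes | yes |
| Fall outside a session | no | no | yes, the only route |

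The gap is therefore confined to falls outside sessions.

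**Illustrative number of people who fall**

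Inputs: 70% with a fall within a year of stroke (Background); 6 weeks of treatment (Intervention); 40 participants (Randomisation, blinding, and concealment). Assumption: a constant rate over the year that also applies to these participants.

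- Weekly rate = −ln(1 − 0.70)/52 = 1.204/52 = 0.0232.
- Six-week risk = 1 − exp(−6 × 0.0232) = 13.0%; 0.130 × 40 = 5.2 participants.
- At half that rate: 1 − exp(−6 × 0.0116) = 6.7%; 0.067 × 40 = 2.7 participants.

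These are falls of any severity, inside or outside sessions. The number both outside a session and graded moderate or severe would be smaller; the protocol gives no share for either.

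**Comparison with Table 1**

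20% of 40 is 8, so Proceed requires at most 7 participants with a moderate to severe event. Even if every one of the estimated 3 to 5 people had a moderate or severe fall and none was recorded, the falls alone would not reach 8.

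**Sensitivity to incomplete capture in general**

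Let p be the true proportion with a moderate to severe event and s the share of those participants recorded. Then P(Proceed) = P(X ≤ 7) with X ~ Binomial(40, p·s). Both p and s are assumptions.

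| p | s = 1.00 | s = 0.90 | s = 0.75 | s = 0.50 |
|---|---|---|---|---|
| 0.20 | 0.44 | 0.57 | 0.76 | 0.96 |
| 0.25 | 0.18 | 0.29 | 0.52 | 0.88 |

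Here s applies to participants with any qualifying event. Missing only out-of-session falls would lower s by less than the right-hand columns suggest. The table shows that completeness matters to this criterion, not that capture will be poor.

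**The case against.** The strongest defence is that nothing in the protocol is contradicted. The form is titled for events following stimulation and does that job; its open row accepts any event and carries the same columns; and the list has a stated basis in reviews that cannot be checked here. In-session falls, the ones most directly tied to training, have their own route. All of this stands, and it limits the point to falls outside sessions. It does not show that the harms of the training component were considered when the list was made: the systematic review is described as covering taVNS, and the scoping review's coverage is not stated.

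Three stronger readings are tempting, and the documents do not support them.

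- A reader might infer that the Background names cardiac and voice events as relevant to this intervention. It does not. The sentence reads "iVNS is costly and requires a surgical procedure, limiting accessibility and imposing potential safety risks including symptomatic bradycardia, localised infection, and transient vocal cord palsy", so these are risks of the implanted device. taVNS is then said to be one that "has been used successfully as a non-invasive, and potentially, safer alternative to iVNS". Dizziness already has a row.
- A reader might infer that falls will be under-counted. The documents give no capture rate, and a route for reporting exists. Less complete capture is possible but not demonstrated.
- A reader might infer that missed falls alone could move the Table 1 result to another band. On the figures above they could not; other events would also have to be close to the limit.

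The 70% is also a weak basis for a rate in this trial. It refers to the first year after stroke, whereas participants enter at least 6 months after stroke.

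**Conclusion.** The point holds in a limited form. Appendix 1 prompts for ten symptoms oriented to stimulation and not for falls, in a trial that trains gait and balance in people impaired in both or either. Falls outside sessions depend on one free-text row of a form that asks only about stimulation, so they may be recorded less completely than listed symptoms. The likely size is small: roughly 3 to 5 of 40 participants with any fall over six weeks, under a constant-rate assumption that probably errs high, and fewer with an out-of-session fall graded moderate or severe. This is a cheap improvement to an instrument fixed in the protocol, not an error that undermines the trial. It is worth making because safety is part of the primary aim and the Table 1 adverse event row is not limited to stimulation-related events.

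**What to change.** Add one prompted row to Appendix 1, 'Fall (during or outside a session)', using the existing severity grades. For this row, let relatedness be marked separately for stimulation and for the training, because the present columns ask only about stimulation and do not suit a fall at home. Keep the open row for everything else. Use the same form in both arms, so that falls are elicited alike under active and sham stimulation.

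The cost is one row and one extra tick box on an existing form. The recorded event rate may rise slightly, which should be remembered when the Table 1 limits are read and when results are compared with studies that did not prompt for falls.

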Appendix 2. Interview guide

The effect of non-invasive auricular vagus nerve stimulation paired with physiotherapy on gait and balance impairments in chronic stroke: Phase 2-randomised controlled feasibility trial

Interview Guide

Please note that this interview is being recorded and will be transcribed for analysis. Do you consent to this?

Qu 1: How did you find your experience with using the non invasive auricular vagus nerve stimulation?

Qu 2: What things did you like about using non invasive auricular vagus nerve stimulation?

What things didn't you like about using non invasive auricular vagus nerve stimulation?

Qu 3: For the therapy sessions you were not able to complete, what would you say was the major factor preventing you from doing so?

Qu 4: Do you think your balance and mobility has changed since your stroke? In what way has it changed and do you think it was because of the non invasive auricular vagus nerve stimulation?

Qu 5: Has your participation in activities changed since your stroke? What is your opinion about the role of non invasive auricular vagus nerve stimulation in these changes?

Qu 6: If you were given the opportunity would you continue to use taVNS after this treatment finished?

Qu 7: How would you rate the comfort/ability to tolerate the device/stimulation?

Qu 8: Do you think using equipment such as non invasive auricular vagus nerve stimulator in the future in clinics or at home would be worthwhile?

Qu 9: Are there any other comments you would like to make about your participation and experience in the trial?

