Study Design: This will be a randomised double-blinded sham-control trial. Participants will be assessed at baseline, immediately post, and at \geq 30 days after completing the intervention.

Participants:

Participants will be recruited from the UniSA Health and Medical Clinic as well as advertising at Stroke SA, Stroke Foundation and via social media. All assessments and treatments will be conducted within the UniSA Health and Medical Clinic at the City West.

Power and sample size: A power calculation is not necessary for a feasibility study; further no studies have investigated the use of taVNS for enhancing gait and balance. However, to provide some insight, we have performed a power calculation based on effect sizes obtained from a previous upper limb taVNS study [10]. It was determined that 18 participants will be required (in each group) to detect a moderate effect size of 0.70, given an alpha level of 0.05 and power of 80 % [15].

Inclusion criteria: Aged 18 years or older; first-ever haemorrhagic or ischaemic stroke at least 6 months earlier; can walk 10 meters with or without a gait aid and with or without assistance (assessed using 10-meter walk test [16]), no history of other neurological conditions; gait and/or balance impairment; ability to give informed consent and to understand instruction.

Exclusion criteria: Previous vagus nerve surgery; cognitive impairment and/or language impairment that might impact the person's ability to consent or understand instructions (MOCA score of less than 18); severe pain in any joints of the affected limb; advanced cardiac, pulmonary, kidney or liver condition; pregnancy; use of neuroactive medication [6]; active implants; cerebral shunts; open skin at the point of stimulation.

Intervention: The physical rehabilitation therapy component of the intervention will be tailored to participants' impairments and goals. It will consist of 15 sessions conducted over 6 weeks (2-3 x 1-hour sessions per week). Concurrently with the physical rehabilitation, participants will receive one of taVNS conditions (active or sham, allocation will be randomised).

taVNS stimulation parameters:

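### Interview questions 4 and 5 date change from the stroke rather than from the start of trial treatment, and name only the stimulation as a cause, so answers on perceived change will be hard to interpret

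*Protocol*

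**What the plan says.** The Protocol lists participants' experience with taVNS as an outcome (Outcome Measures, item 3). It is collected in a structured interview of every participant, 5 days after the last treatment session, using the guide in Appendix 2. The Statistical analysis section assigns the interviews to thematic analysis.

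Two of the nine numbered questions concern change:

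- Question 4 opens with "Do you think your balance and mobility has changed since your stroke" and continues "In what way has it changed and do you think it was because of the non invasive auricular vagus nerve stimulation".
- Question 5 opens with "Has your participation in activities changed since your stroke" and continues "What is your opinion about the role of non invasive auricular vagus nerve stimulation in these changes".

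Three other parts of the Protocol bear on how these will be answered:

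- **Eligibility:** the criterion is "first-ever haemorrhagic or ischaemic stroke at least 6 months earlier", with no upper limit on time since stroke.
- **Recovery:** the Background says "Recovery from stroke mainly occurs in the subacute stage".
- **Intervention:** of the physical rehabilitation, the Intervention section says "It will consist of 15 sessions conducted over 6 weeks". On the stimulation it adds "Concurrently with the physical rehabilitation, participants will receive one of taVNS conditions", active or sham.

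**The concern.** The interview is meant to show what participants made of the trial treatment, but its two change questions start the clock at the stroke. In each, the follow-up on taVNS refers back to the whole of that change. A participant may be thinking of what the stroke took away, of recovery in the first months, of earlier therapy, or of the 6 weeks in the trial. The wording does not tell these apart.

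The follow-ups also name one candidate cause only. Stimulation and rehabilitation are given together in both arms, so someone who noticed a change during the trial is asked about the device and not about the exercise that came with it.

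What is at stake is the value of the themes on perceived change. This is a feasibility trial and those themes may inform a later one. Each participant is interviewed once, soon after treatment ends, so a poorly framed answer is not easily replaced.

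**Working it through.** The Protocol gives no figure on this point to reproduce. The check sets the passages side by side, with one piece of arithmetic for scale.

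**Step 1: what the follow-ups refer to.** In question 4 the pronoun in the second sentence can only refer to the change since the stroke. In question 5 the follow-up points to the changes just named. In both, the participant's view of taVNS is tied to the full period since the stroke.

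**Step 2: what lies in that period.** In order of time:

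1. the deficit caused by the stroke;
2. the subacute stage, where the Background places most recovery;
3. any earlier rehabilitation;
4. the 6-week trial treatment;
5. the 5 days before the interview.

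The minimum of 6 months from stroke to entry puts the stroke's own loss and the main recovery before any trial stimulation.

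**Step 3: whether another question supplies the missing reference point.** The other questions cover experience with the device, likes and dislikes, sessions not completed, willingness to continue, comfort, future use and any other comments. None asks about change over the treatment period. The interview is structured, so the printed wording is what participants should be expected to hear.

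**Step 4: whether another cause is offered.** Questions 4 and 5 name the stimulation only. Neither mentions the rehabilitation sessions or asks openly about cause.

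**Step 5: scale.** Share of the period asked about that is trial treatment = 42 days ÷ (days from stroke to start of treatment + 42 + 5).

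| Time from stroke to start of treatment | Calculation | Share |
|---|---|---|
| 6 months (183 days), the Protocol's minimum | 42 ÷ (183 + 42 + 5) = 42 ÷ 230 | about 18% |
| 2 years (731 days), assumed | 42 ÷ (731 + 42 + 5) = 42 ÷ 778 | about 5% |
| 5 years (1,826 days), assumed | 42 ÷ (1,826 + 42 + 5) = 42 ÷ 1,873 | about 2% |

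The first row is a ceiling, because nobody can enter earlier. The other two are illustrations, because the Protocol gives no distribution of time since stroke. For every participant, about four fifths or more of the period lies outside treatment (1 − 0.18 = 0.82). These are shares of calendar time. They do not measure how much perceived change is misattributed.

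**Step 6: what depends on the answers.** Table 1 uses consent, completion, Likert ratings, blinding and adverse events, and questions 4 and 5 produce none of these. Safety has its own weekly questionnaire (Appendix 1) and blinding has another (Appendix 3). Efficacy rests on measured outcomes at three time points, compared between arms in a linear mixed model.

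**The case against.** The strongest reply is that the questions do not credit the device with anything. Question 4 asks whether the participant thinks taVNS was the reason, and question 5 asks for an opinion on its role. Both leave room for a plain no. Participants interviewed days after their last session may well separate what happened before the trial from what happened in it, and question 4 invites them to describe the change. Asking about taVNS suits the stated purpose of the interview, and question 9 leaves room for anything else.

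Much of this stands. A reader might infer that the questions attribute change to taVNS, or that they cannot yield any perceived effect of treatment. The wording supports neither: it makes answers noisier and more ambiguous, not useless.

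A reader might also infer that the themes will lean towards benefit. The documents do not support that. The period includes the stroke's own loss, and eligibility requires a current gait and/or balance impairment, so some participants will describe worsening that nobody would credit to the device. Both arms get the same questions, so any inflation need not favour active treatment. That some participants receive sham is the control condition and not a fault of the question.

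The reply does not supply a reference point for change during treatment. No question gives one, and a catch-all closing question in a structured interview is a weak substitute.

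**Conclusion.** The point holds as a minor defect of wording in two of nine interview questions. As written, answers can mix the initial deficit, earlier recovery and prior rehabilitation with the 6-week treatment, and they do not separate stimulation from the rehabilitation given with it. Themes on perceived change will be hard to interpret, and the direction of any distortion is unknown.

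The only figure that rests on the Protocol alone is the ceiling of about 18% of calendar time, taking 6 months as 183 days and treatment as 42 days. It shows that the period asked about is far longer than the period of interest, and no more.

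A reader might infer that the efficacy or feasibility conclusions are at risk. They are not: no Table 1 criterion, safety summary or mixed-model comparison uses these answers.

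**What to change.** In Appendix 2, change the reference point in both questions to the start of study treatment, and ask about cause openly before naming any candidate. For example:

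- **Question 4:** *Has your balance or mobility changed since you started this study's treatment? In what way? What do you think contributed to this?* Then, as separate probes: *Did the stimulation play a part? Did the physiotherapy play a part?*
- **Question 5:** the same sequence for participation in activities.

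The new reference point is the essential change. The open question and the two separate probes deal with the single-cause prompt.

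The cost is two reworded questions and an ethics notification. Treatment, sample size, visit schedule and quantitative analysis stay as they are. If interviews have already been held with the present wording, report which version each participant answered and interpret the earlier answers on change with that in mind.
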